4.1 Descriptive analysis

4.1.1 Inclusion

The total number of:

- included patients,
- patients included in the safety analysis,
- patients included in the efficacy analysis

We also describe deviations regarding eligibility criteria. A listing of patients with major protocol deviations including subject ID and type of deviation.

4.1.2 Baseline characteristics

The following data will be presented for the global population and for the efficacy population.

Baseline evaluation

- Demographic data: sex, age
- Vital signs : height, weight, ECOG performance status, pulse, O₂ saturation, body temperature, and dystolic/systolic blood pressure
- Genetic mutations: BRCA1, BRCA2

History of disease

- Delay between date of diagnosis and date of inclusion
- Delay between date of disease diagnosis and date of diagnosis of the metastatic disease (or advanced disease if not metastatic)
- Delay between date of the last disease progression before inclusion and date of inclusion
- Clinical characteristics: tumor form, laterality, clinical size, TNM staging, and SBR
- Pathological examinations: pathological tumor size, histological tumor size, number of nodes involved and removed,
- Hormonal receptors status: estrogen, progesterone, androgen, IHC, amplification (if IHC 2+)
- Metastatic site at inclusion

History of treatment

- Neoadjuvant treatment (hormone therapy, chemotherapy)
- Adjuvant treatment (hormone therapy, chemotherapy)
- Radiotherapy
- Surgery
- Other

Significant medical and surgical history

The symptoms present at inclusion will be described in terms of:

• Number of patients with at least one symptom

• Number of patients with at least one grade \geq 2 symptom

Protein expression study: immunohistochemistry

Immunohistochemical staining will be performed on FFPE biopsy samples. The frequencies and other characteristics of positive tumor markers (P4EBP1, PTEN, pAKT, pS6RB, LKB1) will be presented.

The ALLRED score will be calculated as follows:

- < 10% : score 0 + intensity value (0 to 3)

- 10-30%: score 1 + intensity value (1 to 3)
- 30-50%: score 2 + intensity value (1 to 3)
- 50-70%: score 3 + intensity value (1 to 3)
- 70%-100%: score 4 + intensity value (1 to 3)

The ALLRED score is between 0 and 7.

Laboratory tests

- Complete blood count (CBC): hemoglobin, platelets, leucocytes, and neutrophils
- Coagulation: prothrombin time, partial thromboplastin time, and international normalized ratio
- Blood electrolytes: calcium and phosphorus
- Kidney function: creatinine and creatinine clearance
- Liver and pancreas function: AST, ALT, total bilirubin

4.1.3 Study treatment administration

The following data will be summarized for each treatment (exemestane and everolimus):

- Number of patients who received at least one dose of treatment
- Treatment duration
- Dose received at treatment initiation
- Number of patients with at least one dose modification (Yes/No) and reason
- Number of patients with definitive discontinuation of study treatment (Yes/No) and reason

Note that the end of treatment is defined as the date at which everolimus was discontinued (for whatever reason), or when a new antineoplastic treatment is initiated. A definitive discontinuation of exemestane is not considered as a discontinuation of study treatment.

4.1.4 End of study

Number of patients having terminated/withdrawn from the study and associated reason.

4.2 Efficacy endpoint

4.2.1 Primary endpoint

For the primary endpoint, the analysis will be performed on the efficacy population and will include all treated and evaluable patients. A patient will be considered as evaluable if 1) no major violation of eligibility criteria, 2) the patient has received at least one dose of everolimus, 3) the patient has at least one tumor evaluation performed before and another 6 months after treatment initiation and 4) an expression levels of p4EBP1 is available for the patient. The clinical benefit rate at 6 months (CBR-6m) will be defined as the proportion of patients with a complete response, a partial response, or a stable disease 6 months after initiation of treatment. The CBR-6m and its associated 95% confidence interval (CI) will be described globally and according to high vs low p4EBP1 expression, and will be compared between the 2 subgroups using a chi-square test. In the absence of assumptions, the choice of cut-off for dichotomized the population depending on p4EBP1 values will be done using the median value of the biomarker distribution, the aim being to consolidate data into subgroups of comparable strengths to maximize the power. A second cut-off will be determined using the X-tile software, proposing a division of the population for an optimal separation of data seeing the responses. This second analysis will be considered as a sensitivity analysis.

Logistic regression analyses will be performed to assess the predictive potential effect of biomarker level on clinical benefit rate at 6 months (Yes/No). Clinical factors known to be predictive of clinical benefit will be added to the model to verify the independence of the marker. A step-by-step descending selection of variables will be used to retain factors that were independently linked to clinical benefit. All variables sufficiently informed (with <10% missing value) and significant (at 15% level) in the univariate approach will be introduced in the initial multivariate model. The final multivariate model will be include only variables which will be statistically significant at a 5% threshold. Odd ratio (OR) will be presented with 95% confidence interval (CI). A p-value <0.05 will be considered statistically significant.

For each patient, the variable "clinical benefit rate at 6 months Yes/No" will be determined as follows:

- (1) if a progression is recorded in the tumor evaluation form and if the duration between treatment initiation (everolimus) and the first documented progression is ≤7 months, then the variable "clinical benefit rate at 6 months" will be set to "no"
- (2) if condition (1) is not fulfilled and a complete response, a partial response or a stable disease is recorded in the tumor evaluation form, and if the duration between treatment initiation (everolimus) and the tumor evaluation form is ≥5 months, then the variable "clinical benefit rate at 6 months" will be set to "yes"
- (3) if condition (2) is not fulfilled and if we have no tumor evaluation between 5 and 7 months after treatment initiation and patient is non progressive or without tumor evaluation before 5 months but progressive after 7 months, or non-progressive in last evaluation occurring within 5 months then the primary endpoint "clinical benefit rate at 6 months" will be defined patient by patient during blind review but blinded to p4EBP1 level.
- (4) if condition (3) is not fulfilled and if the patient died before 7 months from other cause than clinical progression, then the variable "clinical benefit rate at 6 months" will be set to "Not Available".

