2.2 Study endpoints

2.2.1 Primary endpoint

The primary endpoint of the trial is the predictive value of p4EBP1 in determining mTOR inhibitor efficacy, measured by the association between expression level of the biomarker (high vs low expression) and clinical benefit rate (CBR) 6 months after initiating EVE-EXE treatment. Clinical benefit at 6 months is defined as a complete or partial response or stable disease at 6 months after treatment initiation.

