3.1 Sample size

The primary endpoint of the study is the association between expression levels of p4EBP1 (high vs low expression) and clinical benefit after 6 months of EVE-EXE treatment (CBR-6m).

We plan to enroll 150 patients in the study in order to have a minimum of 120 patients evaluable for the primary endpoint (some patients may not be evaluable: their tumor samples may not being analyzable, patients may not have been treated with the treatment combination [EVE-EXE]...).

With a sample size of 120 patients (60 patients in each subgroup defined by low vs high expression), a twogroup chi-square test with a 0.05 two-sided significance level will have 80% power to detect an increase in CBR at 6 months corresponding to an odds ratio of 2.8 (from 30-40% in p4EBP1- group to 55-65% in p4EBP1+ group). We estimate that this benefit, compared with those observed in the TAMRAD study (Bachelot, 2012), will reflect a clinically meaningful predictive value of the studied biomarker.

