3.2 General statistical methods

Quantitative data will be described using the number of observations, mean, standard deviation, median, minimum and maximum values.

Qualitative variables will be described using frequency and percentage distributions. The number of missing data will be given, but will not be considered for the calculation of proportions.

All confidence intervals and statistical tests will be 2-sided and performed at a 5% level. P-values \geq 0.001 will be reported to 3 decimal places; p-values less than 0.001 will be reported as "<0.001".

Statistical analyses will be performed using SAS® software version 9.4.

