4.2.2 Secondary endpoints

- **Progression-free survival (PFS)** will be measured from the date of treatment initiation to the date of event defined as the first documented disease progression or death from any cause. Patients with no event at the time of analysis will be censored at the date of last adequate tumor assessment. The date of first progression will be determined using data from the tumor evaluation form.
- **Overall survival (OS)** will be measured from the date of treatment initiation to the date of death from any cause. Patients who are alive at the time of analysis will be censored at the date of last contact. Number of patients deceased and cause of death will be reported.

PFS and OS will be estimated using the Kaplan-Meier method. Survival curves will be plotting according to p4EBP1 (high vs low) and compared using a logrank test.

A Cox proportional hazards model will be performed to explain the progression-free survival time. Variables sufficiently informed (less than 10% missing values) and significant at a 15% level in a univariate approach will be included in a backward selection procedure to keep factors significant at a 5% level in the final multivariate model. Hazard ratios (HRs) will be presented with their 95% confidence intervals (CI).

- The clinical benefit rate at 6 months will be described with its 95% confidence interval according to:
 - the presence/absence of each studied genomic event
 - the expression levels of each studied proteomic biomarker (cutoff will be defined in the same way as mentioned for the primary endpoint)
- Descriptive statistics will be used to **characterize the molecular landscape** of endocrine-resistant disease in terms of genomic events observed. Correlations between the different types of genomic events will be studied.

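### The X-tile cut-off is chosen on the responses it is then judged against, so it is an exploratory analysis and not a sensitivity analysis

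*SAP*

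**What the plan says.** SAP 4.2.1 compares CBR-6m between high and low p4EBP1 with a chi-square test and sets the primary cut at the median of the marker, which does not use the outcome. A second cut then comes from X-tile, "proposing a division of the population for an optimal separation of data seeing the responses". On its status the SAP says: "This second analysis will be considered as a sensitivity analysis".

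Only one efficacy population is defined (3.3), so the second cut is chosen and evaluated in the same patients. The SAP mentions no validation sample, permutation, adjusted p-value or shrinkage, and does not give X-tile's search criterion or settings. The general rule in 3.2 is: "All confidence intervals and statistical tests will be 2-sided and performed at a 5% level". For the other protein markers, 4.2.2 states: "cutoff will be defined in the same way as mentioned for the primary endpoint". The marker scale is given in 4.1.2: "The ALLRED score is between 0 and 7".

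**The concern.** A sensitivity analysis is useful only if it could disagree with the primary result. A cut picked because it separates responders from non-responders in these patients will separate them well whether or not the marker carries information. A reader who trusts the label would take agreement at the X-tile cut as confirmation of a positive primary result, or as rescue of a negative one. An unadjusted p<0.05 there, or the CBR difference and its confidence interval, would overstate the evidence for p4EBP1.

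**Working it through.** **Inputs.** From SAP 3.1: 120 evaluable patients, 60 per subgroup, two-sided 5% chi-square test, 80% power, CBR "from 30-40% in p4EBP1- group to 55-65% in p4EBP1+ group". From 4.1.2: a score from 0 to 7, hence at most 7 cut points. Assumed, because the SAP does not give them: the distribution of the score, the minimum group size and X-tile's criterion.

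**1. The SAP's own power figure.** Power = Φ[(|p2−p1|√n − 1.96√(2p̄q̄)) / √(p1q1+p2q2)]. For 35% vs 60% and n = 60, p̄ = 0.475. This gives (1.936 − 1.384)/0.684 = 0.808, a power of 79.0%. For 30% vs 55% it is 79.9%. The stated 80% is reproduced, and 47.5% serves as the null CBR below.

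**2. What holds by construction.** Let X²(c) be the CBR-6m chi-square at cut c. If the search maximises X²(c) and the median cut m is a candidate, then max X²(c) ≥ X²(m). So X²(m) > 3.84 implies that the chosen cut also exceeds 3.84. Under this criterion a positive primary result can never be contradicted.

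**3. Size under no association.** With 7 cuts, each tested at 5%, the chance that at least one is significant is at most 7 × 5% = 35%. It is lower in practice because the tests are correlated. Simulation used 20,000 trials per cell with n = 120 and CBR 47.5%. The spread scores were uniform, bell-shaped (centre 3.5, SD 1.7), and 30% at zero with 10% at each other value. Independent re-runs gave the same score figures within simulation error.

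| Best cut by chi-square | p<0.05 at the chosen cut |
|---|---|
| Spread scores, groups of at least 10-20% | 12-21% |
| Spread scores, no minimum group | 20-23% |
| Peaked score (55% at one value), groups of at least 10% | 13% |
| Peaked score, groups of at least 20% | 7% |
| Continuous marker, groups of at least 10-20% | 33-43% |
| Median split, for comparison | about 5% |

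For the spread scores with groups of at least 10-20%:

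- Significant in favour of high expression: 6-11%.
- Significant although the median split was not: 7-17%.
- Nominal 95% CI for the CBR difference covers zero: 75-87%.
- Mean absolute CBR difference: 12-17 points. At the median it is 7, which theory confirms: √(0.475 × 0.525 × 2/60) × √(2/π) = 0.0912 × 0.798 = 7.3 points.
- True 5% threshold for the maximised chi-square: 5.5-6.6 instead of 3.84. An unadjusted p of 0.05 is therefore an adjusted 0.12-0.21.
- With a null CBR of 35% or 60%, the rejection rate is again 12-21%.

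**4. Other search criteria** (spread scores, same group limits, null).

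| Criterion | p<0.05 at the chosen cut | Chosen cut significant when the median split is |
|---|---|---|
| Largest CBR difference | 12-19% | 87-98% |
| Youden index | 12-20% | about 100% |
| Largest PFS log-rank | 9-15% | 71-84% |

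**5. When the marker does work.** With a true step from 35% to 60% placed at score 3, 4 or 5, the difference at the chosen cut exceeds the true difference at that cut by 2-5 points on average. The median split has about no such bias. On the odds-ratio scale, with a uniform score and the step at its middle (true OR 2.79), the geometric mean OR is 3.1 at the chosen cut and 2.7 at the median.

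**6. Correction.** Permuting the outcome and repeating the whole search brings the size back to 4-5% on the spread scores and 5-6% for a continuous marker.

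**The case against.** The strongest reply is that nothing decisive rests on this analysis. The primary cut ignores the outcome and the median-split test keeps its error rate. That stands, and it limits the point to a supporting analysis.

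The SAP also names no test at the second cut. A chi-square, as at the median, is the natural reading but an inference, so the rejection rates are conditional on it. The optimism of the CBR difference and its interval needs no such inference and is the firmer part.

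X-tile's criterion and settings are unknown, and silence on correction is not a refusal to correct. The null rates move from 7% to 43% across the assumptions tabulated. The continuous case deserves little weight, since the SAP defines a 0-7 score. If the search used PFS, the chosen cut would fail to confirm a significant median split in 16-29% of null trials, so agreement there is usual and not assured.

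Finally, the second cut has a legitimate use. If the true step lies away from the median, the median split understates the 25-point difference, by 0 to 11 points in the scenarios run, while the optimal cut is off by −0.2 to +2.4 points. With a bell-shaped score and the step at 3 or 5, the median split detects it in 32-33% of trials and the unadjusted optimal cut in 72-76%. A non-significant optimal cut would also support a negative primary result. These are reasons to keep the analysis under a correct label, not to keep the present label.

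**Conclusion.** The concern holds. The X-tile contrast is selected on the outcome in the patients in whom it is reported, so it is biased away from the null. It cannot challenge a positive primary result if the search maximises the CBR-6m chi-square with the median among the candidates, and it challenges one only in a minority of trials under the other criteria examined.

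On the 0-7 score with spread distributions and groups of at least 10-20%, the nominal 5% error becomes 12-21%, and the typical null difference roughly doubles, from 7 to 12-17 points. These are illustrations, not bounds: they assume the score distributions, the group limits and a chi-square test at the chosen cut, and the inflation shrinks when few cuts are admissible. The primary test is unaffected, so this should be corrected but does not threaten the main conclusion. For the other protein markers in 4.2.2 only descriptive CBRs and intervals are planned. The point is minor there and arises only if the X-tile cut is used.

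**What to change.** In SAP 4.2.1, replace the sentence that labels the second analysis with:

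> This second analysis is exploratory. Either no p-value or only a selection-adjusted one will be reported, from a permutation that repeats the whole cut-off search (for example, of the maximally selected chi-square). The CBR difference, odds ratio and confidence intervals at this cut are optimistic because the cut was selected on the outcome.

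Apply the same label to any X-tile cut used under 4.2.2. If a sensitivity analysis of the cut-off is wanted, choose one that does not depend on the outcome, for example the p4EBP1 score as an ordinal or linear term in the logistic model. That may already be intended: the logistic paragraph of 4.2.1 refers to the marker's level without saying whether this is the score or the dichotomy, while 2.2.1 points to high versus low. State which.

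The cost is two sentences and, if a p-value is kept, a short permutation loop. The X-tile result will look less favourable.

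### The logistic model meant to verify p4EBP1's independence selects both the marker and the clinical factors by p-value, so the adjusted odds ratio may be missing or unadjusted

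*SAP*

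**What the plan says.** Section 4.2.1 of the SAP has two layers. The primary comparison is unadjusted: CBR-6m is described by p4EBP1 group (split at the median) and "will be compared between the 2 subgroups using a chi-square test".

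A supportive model follows: "Logistic regression analyses will be performed to assess the predictive potential effect of biomarker level on clinical benefit rate at 6 months (Yes/No"). Its purpose is stated: "Clinical factors known to be predictive of clinical benefit will be added to the model to verify the independence of the marker".

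The section then fixes how the model is built, by backward selection in two filters:
- Entry: "All variables sufficiently informed (with <10% missing value) and significant (at 15% level) in the univariate approach will be introduced" in the initial multivariate model.
- Retention: "The final multivariate model will be include only variables which will be statistically significant at a 5% threshold".

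No sentence exempts p4EBP1 or the known clinical factors from either filter, and none says what is reported if the marker, or every factor, drops out. The Cox model for PFS in section 4.2.2 uses the same two thresholds.

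**The concern.** The aim and the method do not match. To verify that a marker is independent of known factors, the marker and those factors must be in the same model. Selection by p-value does not ensure this, and it can fail in two ways.

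1. If p4EBP1 misses a threshold, the final model contains no odds ratio for it. The reader does not learn how large the adjusted association was or how uncertain it is.
2. If a clinical factor misses p<0.05, it leaves the model even when it is a real confounder. The marker is then called independent of factors it was not adjusted for.

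The high and low groups come from a median split, not randomisation, so they may differ in prognosis. For clinical benefit at 6 months, this model is the SAP's only stated check that clinical factors do not explain the association.

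**Working it through.** **Inputs from the SAP (section 3.1).** "With a sample size of 120 patients (60 patients in each subgroup defined by low vs high expression"); a "chi-square test with a 0.05 two-sided significance level will have 80% power"; an effect "corresponding to an odds ratio of 2.8 (from 30-40% in p4EBP1- group to 55-65% in p4EBP1+ group"). The thresholds of 15% and 5% are from section 4.2.1. The SAP gives no covariate structure, so everything about the clinical factors in steps 3 to 5 is assumed.

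**Step 1: reproduce the stated power.** With n per group, p̄ the mean of p1 and p2, and no continuity correction:

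z = [ |p2 − p1|·√n − z(α/2)·√(2p̄(1−p̄)) ] / √( p1(1−p1) + p2(1−p2) )

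- 30% vs 55% (odds ratio 2.85): z = (0.25·√60 − 1.96·√0.48875) / √0.4575 = (1.9365 − 1.3702) / 0.6764 = 0.837; power 79.9%.
- 35% vs 60%, and likewise 40% vs 65% (odds ratio 2.79): power 79.0%.
- Exactly 2.8 from 30% or 40%: power 78.4% or 79.4%.

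The stated 80% is reproduced to within 2 points.

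**Step 2: how often the marker survives.** This needs only the SAP's inputs. At the design effect the marker passes the 15% screen with probability about 91%, but reaches p<0.05 with probability only 78–80%. It is therefore absent from the final model in about 1 − 0.80 = 20% to 1 − 0.78 = 22% of trials in which the design effect is true.

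**Step 3: how often a real factor survives.** For a binary factor split 60/60, the same formula gives p<0.05 in 44–47% of trials at odds ratio 2.0 and in 18–19% at 1.5. It is omitted in 53–56% and 81–82%.

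**Step 4: both filters together, three assumed factors.** Simulation with n = 120, factors at 50% prevalence, either unrelated to the marker or differing by 20 points between marker groups, 2,000 trials per scenario.
- Marker absent: 18–27% at true odds ratio 2.8; 46–58% at 2.0; 73–83% at 1.5.
- Marker retained but adjusted for no factor: 19–34% of retained cases with factor odds ratios of 2.0; 54–71% with 1.5.
- Marker odds ratio averaged only over trials that retain it: 3.3–3.9 for a true 2.8. With marker and factors always kept: 2.91–2.94.

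**Step 5: five assumed factors, three rules on the same data.** Factor odds ratios 2, 2, 1.5, 1, 1; CBR 35% in marker-negative patients; true marker odds ratio 2.8; 5,000 trials per main scenario and 3,000 per added one. An associated factor has prevalence 65% vs 35% between marker groups.

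*Literal rule.* No adjusted odds ratio for the marker in 22–24% of trials. In a further 18–28% the marker stays but no clinical factor does.

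*Marker locked in, factors still selected.* A factor with true odds ratio 2 is omitted in 58–61% of trials, and no factor remains in 25–30%. Geometric-mean odds ratio and 95% CI coverage:

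| Factors associated with the marker | Factors selected | All forced in |
|---|---|---|
| none | 2.9, 95% | 3.0–3.1, 95% |
| one | 3.1, 93% | 3.0–3.1, 95% |
| two | 3.3–3.4, 90–91% | 3.0–3.1, 95% |
| all five | 3.5, 88% | 3.0–3.1, 95% |
| two, opposite direction | 2.4, 90% | 3.0–3.1, 95% |

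At a true marker odds ratio of 1, the locked marker has p<0.05 in 5%, 10% and 15% of trials with 0, 2 and 5 associated factors, against 5% with all forced in. Repeat runs of 2,000 trials with 2 and 5 associated factors gave odds ratios of 3.4–3.6, coverage of 88–90% and false positives of 11–14%.

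*Weaker association, marker locked in.*
- 10 points (55% vs 45%), two associated factors: 3.02 with 95% coverage selected, 3.01 with 95% forced.
- 10 points, five associated factors: 3.09 with 95% selected, 3.01 with 96% forced.
- 10 points, true odds ratio 1: p<0.05 in 4.6% (two factors) and 6.4% (five) with selection, against 4.6% and 5.2% forced.
- 20 points, two associated factors: coverage 92% selected against 94% forced; p<0.05 at true odds ratio 1 in 7% against 5%.

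**The case against.** Four points can be made for the SAP as written.

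*The text can be read more kindly.* The model starts from the biomarker and the clinical factors are added to it, so selection may be meant for the added factors only. No estimate is then lost. This is possible, but the entry rule speaks of all variables and the retention rule of only significant ones, with no exception. Even on this reading the factors are still removed by p-value, which is the case tabulated in step 5.

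*A dropped marker is itself an answer.* The missing-estimate rate is essentially the rate of a non-significant marker; with no associated factor, the fully forced model is non-significant in 24% of trials too. The CBR by marker group is reported regardless, and the SAP does not rule out showing odds ratios from the univariate or initial models. This stands in part: what is lost is an estimate and its interval, not power. The SAP does not promise the initial model's result, however, and that model exists for the marker only if it passes the 15% screen.

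*The bias needs strong confounding.* This stands. An omitted factor biases the marker's odds ratio materially only if it is also associated with the marker. The effect is negligible at a 10-point difference, modest at 20 points, and marked only when two or more factors differ by 30 points. The SAP gives no information on which applies. That is a reason not to let p-values decide the adjustment.

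*The model is supportive and its rule is declared in advance.* This is true, and it limits the weight of the point. Declaring the rule in advance does not make it suit its stated purpose.

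**Conclusion.** The concern holds. The selection rule in section 4.2.1 can remove the marker, or the factors it is to be tested against, from the model intended to show their independence.

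The loss of the marker's adjusted estimate in about one trial in five follows from the SAP's own sample size and effect. The size of the bias does not: it rests on assumed factors, assumed odds ratios and an assumed association with p4EBP1, and it ranges from nothing to the 88% coverage and 15% false-positive rate of the most heavily confounded case. If no factor is associated with the marker, the missing estimate is the only cost.

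The primary chi-square test, its significance level and the sample size are untouched. The change is worth making because it is cheap and this is the only adjusted check planned for clinical benefit at 6 months.

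**What to change.** Amend section 4.2.1 as follows.

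- Name about five clinical factors known to predict benefit and expected to have under 10% missing values. Do this before p4EBP1 is unblinded, and no later than the start of the patient-by-patient endpoint review that the section already holds blinded to p4EBP1 level.
- Fit one logistic model with p4EBP1 (median cut-off) and these factors, all kept whatever their p-values.
- Report the adjusted odds ratio for p4EBP1 with its 95% CI in every case.
- Keep the stepwise model, labelled exploratory.
- Apply the same to the PFS Cox model in section 4.2.2 only if it is used to assess p4EBP1.

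Six terms are feasible: the step 5 scenarios have 56–63 responders among 120, so the smaller outcome group has at least 56 patients, or 56/6 ≈ 9 per term.

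The cost is SAP wording and some precision. The marker's standard error is about 4%, 8% and 21% larger than in the selected model with 0, 2 and 5 associated factors. At a true odds ratio of 2.8 the forced model is non-significant in 24%, 30% and 41% of trials, against 24%, 18% and 17% with the marker locked and the factors selected. Part of that gap is the selected model's upward bias. A few patients may be lost to missing covariates, so the number analysed should be reported.

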2.1 Study design

The SAFIR-TOR trial is a prospective biomarker study that aims to show that p4EBP1 staining predicts clinical benefit from treatment with the mTOR inhibitor everolimus in patients with locally advanced or metastatic breast adenocarcinoma which cannot be treated with surgery and/or radiation therapy.

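### Rule (2) for clinical benefit at 6 months accepts a response or stable disease recorded after a new antineoplastic treatment began, so another drug's result can count as everolimus benefit

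*SAP*

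**What the plan says.** SAP section 4.2.1 derives the 6-month outcome by four ordered rules.

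- **Rule (1)** scores no if the first documented progression falls within 7 months of starting everolimus.
- **Rule (2)** applies otherwise. It scores yes when "a complete response, a partial response or a stable disease is recorded in the tumor evaluation form", provided that this evaluation took place at least 5 months after everolimus was started. It has no upper time limit and no reference to what the patient is taking at that evaluation.
- **Rule (3)** applies only when rule (2) is not met. It sends missing or ill-timed evaluations to a case review blinded to p4EBP1.
- **Rule (4)** deals with deaths before 7 months not due to progression.

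The efficacy population (sections 3.3 and 4.2.1) asks for minimal exposure: "the patient has received at least one dose of everolimus".

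Section 4.1.3 does define when study treatment ends: when everolimus is discontinued, "or when a new antineoplastic treatment is initiated". That definition serves the description of treatment administration and does not appear in the endpoint rules.

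Section 2.1 says the trial aims to show that p4EBP1 staining "predicts clinical benefit from treatment with the mTOR inhibitor everolimus". Section 2.2.1 speaks of mTOR inhibitor efficacy, and section 3.1 ties the endpoint to 6 months of the everolimus-exemestane combination.

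**The concern.** The endpoint is a tumour status meant to show benefit from one named drug, and the trial's claim is that a marker predicts that benefit. Rule (2) does not separate an evaluation on everolimus from one made on a later drug. A patient who stops everolimus for toxicity or by choice, starts something else and is stable at the next scan is scored as an everolimus success.

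Two results would be affected. The clinical benefit rate, which section 4.2.1 reports overall and by marker group with confidence intervals, would partly describe other treatments. The comparison of marker groups would contain outcomes that say nothing about everolimus.

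**Working it through.** **Does another rule catch the patient?** Take a patient who stops everolimus at month 2 without progression, starts a new antineoplastic drug at month 3, and has stable disease on it at month 6 with no progression by month 7.

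- Rule (1): no progression, so it does not apply.
- Rule (2): stable disease at 5 months or later, so the score is yes.
- Rules (3) and (4): not reached, so the blinded review never sees the case.
- Efficacy population: at least one dose was given and a 6-month evaluation exists, so the patient is evaluable if eligible and with a p4EBP1 result.

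The gap is real on the text. It is limited to patients who switch before a qualifying evaluation and have no recorded progression by 7 months.

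**The plan's own power figure.** Inputs from section 3.1: 60 per group, two-sided 0.05 chi-square test, 30-40% against 55-65%, odds ratio 2.8, power 80%. The formula is power = Φ[(d − 1.96·s0)/s1], where d = p2 − p1, s0 = √(2p̄(1−p̄)/60) and s1 = √((p1(1−p1)+p2(1−p2))/60).

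- 30% v 55%: odds ratio 2.85, power 0.799.
- 35% v 60% and 40% v 65%: odds ratio 2.79, power 0.790.

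The stated 80% is reproduced to within about a point. The sample size is not at fault.

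**Size of the effect (assumed inputs).** The SAP gives no switching rate. Let f = 5-15% of patients in each group switch without recorded progression before a qualifying evaluation. Let q = 30-70% of them be scored as response or stable disease, unrelated to p4EBP1. Let p = 35% and 60% be the rates among the rest.

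- Present rule: rate = (1−f)p + fq.
- Switchers coded no: rate = (1−f)p.
- Difference in the clinical benefit rate = fq, from 0.05 × 0.30 = 1.5 points to 0.15 × 0.70 = 10.5 points.

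| f | Odds ratio, present rule (q 70% to 30%) | Odds ratio, switchers coded no | Power, present rule | Power, switchers coded no |
|---|---|---|---|---|
| 5% | 2.64-2.65 | 2.66 | 0.746-0.748 | 0.750 |
| 10% | 2.50-2.52 | 2.55 | 0.698-0.701 | 0.707 |
| 15% | 2.37-2.39 | 2.46 | 0.647-0.651 | 0.664 |

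Example, f = 15% and q = 70%. Present rule: 0.85 × 0.35 + 0.105 = 40.25% and 0.85 × 0.60 + 0.105 = 61.5%, odds ratio 2.37. Switchers coded no: 29.75% and 51.0%, odds ratio 2.46.

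The two codings differ by 0.01-0.09 in the odds ratio and by 0.2 to 1.7 points of power.

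**If scoring differs by marker group.** Suppose there is no true difference (30% or 40% in both groups), and 5% of non-benefiting patients in one group and 15% in the other are scored yes because of another drug. The test then rejects in 10-12% of trials instead of 5%. This only illustrates direction; nothing in the SAP indicates such a difference.

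**The case against.** **Following patients regardless of a switch may be intended.** Sections 2.2.1 and 4.2.1 define benefit as status 6 months after treatment initiation, with no on-treatment condition. Section 4.2.2 likewise does not censor progression-free survival at new therapy. Rule (2) follows that definition. This is fair, but the SAP does not state the choice. For a tumour-status endpoint meant to show benefit from one drug, it also fits poorly with sections 2.1, 2.2.1 and 3.1.

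**The protocol may close the gap.** The SAP does not say whether scans after a switch are entered on the tumor evaluation form. If they are not, patients last seen without progression before 5 months go to rule (3). This stands as a limit on how many are affected. It does not change what rule (2) says.

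**Coding switchers as no is also imperfect.** A patient who left everolimus in response and stayed stable may carry real everolimus benefit, and a toxicity switch becomes an efficacy failure. This stands, and it is why the present rule should be kept as a sensitivity analysis.

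**Stronger readings to avoid.** A reader might infer that rule (2) causes the whole fall in the odds ratio from 2.79 to 2.37-2.65. It does not: 2.79 is the value when nobody switches, and coding switchers as no still gives 2.46-2.66. Most of the loss comes from switching itself. A reader might also infer that the rate is overstated by 1.5-10.5 points. That holds only if every switcher is a true failure. Against the 47.5% average of 35% and 60%, the present rule moves the overall rate by −2.6 to +3.4 points under the same inputs.

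**Conclusion.** The point holds as a mismatch between the endpoint derivation and the stated aim. As written, rule (2) credits a response or stable disease recorded on a later antineoplastic drug to everolimus, and no other rule catches the case.

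Its size is unknown and may be small. On assumed switching of 5-15% with 30-70% scored as response or stable disease, the clinical benefit rate is 1.5-10.5 points higher than with switchers coded no. The odds ratio is 2.37-2.65 against 2.46-2.66, and power changes by at most 2 points. These figures assume equal switching in both marker groups and outcomes after the switch that are unrelated to p4EBP1.

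The case for change is therefore the validity of the reported rate and of the biomarker claim. The documents do not support a claim that power is materially harmed by the rule, that many patients are affected, or that a false association is likely. This is a cheap improvement.

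**What to change.** In rule (2), count a complete response, partial response or stable disease only if the evaluation precedes any new antineoplastic treatment. In the primary analysis, code patients who started one before a qualifying evaluation at 5 months or later as no.

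Report two sensitivity analyses:

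- the rule as now written;
- these patients referred to the p4EBP1-blinded review of rule (3).

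The cost is a clause in the SAP, one derivation using the new-treatment date that section 4.1.3 already relies on, and two extra analyses. The sample size and patient management do not change. The downside is that switches for toxicity count as failures in the primary analysis; the sensitivity analyses show how much that matters.
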